9.2.4 Clinical Laboratory Assessments

All screening and on-study laboratory samples will be processed and sent to the central laboratory with the exception of erythrocyte sedimentation rate (ESR), urine pregnancy, PPD, and Quantiferon (may be done by central or local laboratory). The central laboratory will be responsible for all screening and on-study serum chemistry,

hematology, serum pregnancy, urinalysis, hepatitis C antibody, hepatitis B surface antigen and core antibody, high sensitivity CRP, and any other laboratory tests required. ESR, urine pregnancy and PPD testing, if applicable, will be performed locally with kits provided by the central laboratory (except PPD). The results of this testing will be maintained in the source documents at the site.

Subjects in the phase 1b part of the study will abstain from strenuous exercise for 72 hours before each blood collection for clinical laboratory tests.

Amgen or designee will be responsible for biomarker and pharmacogenetic assessments, and the central laboratory will ship the samples to Amgen or a specialty laboratory for assay (depending on the assessment). The central laboratory will provide a study manual that outlines handling, labeling, and shipping procedures for all samples. All blood samples will be obtained by venipuncture before investigational product administration. The date and time of sample collection will be recorded in the source documents at the site.

Refer to [Appendix 2](#) for the list of clinical laboratory tests to be performed and to the Schedule of Activities for the timing and frequency.

The investigator is responsible for reviewing laboratory test results and recording any clinically relevant changes occurring during the study in the Event CRF. The investigator must determine whether an abnormal value in an individual study subject represents a clinically significant change from the subject's baseline values. In general, abnormal laboratory findings without clinical significance (based on the investigator's judgment) are not to be recorded as adverse events. However, laboratory value changes that require treatment or adjustment in current therapy are considered adverse events. Where applicable, clinical sequelae (not the laboratory abnormality) are to be recorded as the adverse event.

All protocol-required laboratory assessments, as defined in [Appendix 2](#), must be conducted in accordance with the laboratory manual and the Schedule of Activities.

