10.3.2.3.3 Laboratory Test Results

The analyses of safety laboratory endpoints will include summary statistics at selected timepoints by treatment group. Shifts in grades of safety laboratory values between the baseline and the worst on-study value will be tabulated.

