- The event is to be reported to Amgen as a serious adverse event within 24 hours of discovery or notification of the event (ie, before additional etiologic investigations have been concluded)
- The appropriate CRF (eg, Event CRF) that captures information necessary to facilitate the evaluation of treatment-emergent liver abnormalities is to be completed and sent to Amgen

Other events of hepatotoxicity and potential DILI are to be reported as serious adverse events if they meet the criteria for a serious adverse event defined in [Appendix 4](#)

Additional Clinical Assessments and Observation

All subjects in whom investigational product(s) or protocol-required therapies is/are withheld (either permanently or conditionally) due to potential DILI as specified in [Table 12-2](#) or who experience AST or ALT elevations > 3 x upper limit of normal (ULN) or 2-fold increases above baseline values for subjects with elevated values before drug are to undergo a period of “close observation” until abnormalities return to normal or to the subject’s baseline levels.

Assessments that are to be performed during this period include:

- Repeat AST, ALT, ALP, bilirubin (total and direct), and INR within 24 hours
- In cases of TBL > 2x ULN or INR > 1.5, retesting of liver tests, BIL (total and direct), and INR is to be performed every 24 hours until laboratory abnormalities improve

Testing frequency of the above laboratory tests may decrease if the abnormalities stabilize or the investigational product(s) or protocol-required therapies has/have been discontinued AND the subject is asymptomatic.

Initiate investigation of alternative causes for elevated AST or ALT and/or elevated TBL.

The following are to be considered depending on the clinical situation:

- Complete blood count (CBC) with differential to assess for eosinophilia
- Serum total immunoglobulin IgG, anti-nuclear antibody, anti-smooth muscle antibody, and liver kidney microsomal antibody -1 to assess for autoimmune hepatitis

- Serum acetaminophen (paracetamol) levels
- A more detailed history of:
 - Prior and/or concurrent diseases or illness
 - Exposure to environmental and/or industrial chemical agents
 - Symptoms (if applicable) including right upper quadrant pain, hypersensitivity-type reactions, fatigue, nausea, vomiting and fever
 - Prior and/or concurrent use of alcohol, recreational drugs and special diets

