 - Concomitant use of medications (including non-prescription medicines and herbal and dietary supplements), plants, and mushrooms
- Viral serologies
- Creatine phosphokinase (CPK), haptoglobin, lactate dehydrogenase (LDH), and peripheral blood smear
- Appropriate liver imaging if clinically indicated
- Appropriate blood sampling for pharmacokinetic analysis if this has not already been collected
- Hepatology consult (liver biopsy may be considered in consultation with a hepatologist)

Follow the subject and the laboratory tests (ALT, AST, TBL, INR) until all laboratory abnormalities return to baseline or normal or considered stable by the investigator. The “close observation period” is to continue for a minimum of 4 weeks after discontinuation of all investigational product(s) and protocol-required therapies.

The potential DILI event and additional information such as medical history, concomitant therapies and laboratory results must be captured in the corresponding CRFs.

Approved

Amendment 3

Protocol Title: A Phase 1b/2a Study to Evaluate the Safety and Efficacy of AMG 592 in Subjects With Active Rheumatoid Arthritis With Inadequate Response to Standard of Care Therapy

Amgen Protocol Number AMG 592 20170149

Amendment Date: 06 June 2019

Rationale:

The rationale for this protocol amendment is:

1. To update the phase 1b sample size language throughout the protocol to allow flexibility for expansion and/or addition of cohorts per DLRM recommendation, for replacement of subjects who discontinue investigational drug product prior to completing week 4 of the study and to allow overenrollment of additional eligible screened subjects in each cohort.
2. To expand phase 1b dosing cohorts 2 and 3 by 8 subjects per cohort in order to gain additional pharmacokinetic, pharmacodynamic and safety data at these doses. Due to a large number of early drop outs the pharmacokinetic and pharmacodynamic data from these cohorts was insufficient to understand dose - response relationships.
3. To update the Risks section of the protocol to align with updates to the Investigator Brochure.
4. To update the dose for cohort 3 from [REDACTED] to reflect the DLRM recommendation that this dose be increased.
5. To reduce the thresholds for white blood cell count and absolute neutrophil count in the exclusion criteria because leukopenia is common in this patient population.

Approved

Description of Changes

Section: Global

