9.6.3 Laboratory Test Results

Phase 1b

Unscheduled assessments will be incorporated in the laboratory analyses where possible.

Summaries of chemistry and hematology laboratory data will include baseline value, values and change from baseline at scheduled visits.

Shift tables indicating the change between the baseline and the maximum post dose CTCAE grades **based on CTCAE version 4.0 or later** will be provided for selected laboratory parameters of interest.

A listing of normal ranges of lab analytes will be included. Further, a listing of CTCAE grade 3 or higher laboratory toxicities will be provided for subjects with grade 3 or higher toxicity for any of the parameters included in the shift table. This listing will include all available data for laboratory parameters included in shift table in order to provide proper context. Values outside the normal laboratory reference ranges will be flagged as high or low and corresponding CTCAE grades will be included in the listing.

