Appendix E. Analytical Windows

The last visit with non-missing assessment prior to first dose will be defined as a baseline visit and the analysis visit name will be “Baseline”. For any visit up to Day 1 pre-dose which is not a baseline visit, the analysis visit will be ‘Pre-Analysis’. For post-dose assessments on Day 1 and assessments at Safety follow-up/EOS visit, the analysis visit will be same as the scheduled visit. Only for phase 1b, for post-dose assessments on Day 85 (the day corresponding to week 12 dosing), the analysis visit will be same as the scheduled visit. Remaining visits (scheduled or unscheduled) after Day 1 for any assessment will be mapped to the analysis visit based on visit windows defined in the tables below for that assessment. Only visits applicable for that assessment and phase of the study will be considered for analysis.

Data collected through central lab and local lab will both be mapped into analysis visit windows. The local lab data can only be used in analysis when there is no central lab data available in the analysis visit window.

If more than one visit with non-missing data falls within an analysis visit window, the visit closest to the target day will be considered for analysis. If two visits are equidistant from the target day, the latest visit (or time if on the same day) will be considered. If more than one evaluation has same date and time (for chemistry, hematology or pharmacodynamic results), the value with the smallest accession number will be considered.

Analysis visit windows for selected assessments are included in tables below. For remaining assessments, no visit window will be applied. Day 85 used in Study day window calculation in the tables below is the study day when Week 12 dose was received. If that dose is missing, then 85 is used for calculation.

Phase 1b

Vitals

Analysis Visit	Target Day	Study Day Window
Week 1, Day 2	2	2
Week 1, Day 3	3	3
Week 1, Day 4	4	4-6
Week 1, Day 8	8	7-9
Week 1, Day 11	11	10-12

Analysis Visit	Target Day	Study Day Window
Week n, Day 7*n+1 (n = 2, 3, 4, 5, 6, 7,8, 9, 10)	7n+1	Target day -2, Target day +4
Week 11, Day 78	78	76- (Day 85-3)
Week 12, Day 85 Pre-dose	85	Day 85-2, Day 85
Week 12, Day 86	86	Day 85 +1
Week 12, Day 87	87	Day 85 +2
Week 12, Day 88	88	Day 85 + 3
Week 13, Day 92	92	(Day 85 + 4) -96
Week 14, Day 99	99	97-106
Week 16, Day 113	113	>106

Chemistry, hematology, weight, and ECG (Phase 1b only)

Analysis Visit	Target Day	Study Day Window

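### SAP Appendix E lets a central laboratory result displace a local one without limiting this to by-visit summaries, so a local peak can be lost from the worst-grade shift tables

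*SAP*

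**What the plan says.** SAP Appendix E first assigns results to windows: "Data collected through central lab and local lab will both be mapped into analysis visit windows". It then ranks them by source: "The local lab data can only be used in analysis when there is no central lab data available in the analysis visit window". The next paragraph adds that, when several visits fall in one window, "the visit closest to the target day will be considered for analysis". None of these sentences is limited to a type of table.

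SAP 9.6.3 specifies "Shift tables indicating the change between the baseline and the maximum post dose CTCAE grades" for selected parameters. It also plans a listing of all available data on those parameters, but only for subjects who reach grade 3 or higher on one of them. It brings unscheduled assessments into the laboratory analyses where possible. SAP 9.1 includes unscheduled data by default unless the plan says otherwise. Neither section mentions laboratory source.

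Protocol 10.3.2.3.3 reads: "Shifts in grades of safety laboratory values between the baseline and the worst on-study value will be tabulated". SAP Section 10 records only one change from the protocol's analyses, the dropped ECG listing.

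On where samples go, Protocol 9.2.4 says "All screening and on-study laboratory samples will be processed and sent to the central laboratory", with exceptions only for ESR, urine pregnancy, PPD and Quantiferon. Protocol Appendix 2 allows extra tests at any time. Protocol Appendix 7 asks sites to "Repeat AST, ALT, ALP, bilirubin (total and direct), and INR within 24 hours" during close observation for possible liver injury, without naming a laboratory, and says that "laboratory results must be captured in the corresponding CRFs".

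**The concern.** A maximum post-dose grade is not a by-visit statistic. A sensible rule for choosing one value per visit becomes a filter on the safety data if it is also applied before the maximum is taken.

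Scheduled chemistry and haematology go to the central laboratory, so any local result on those analytes would come mainly from unplanned testing, which is where a peak could lie. ESR, urine pregnancy and PPD are local only, and Quantiferon is a screening test. After dosing, the central-over-local rule therefore has work to do mainly for chemistry and haematology.

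Laboratory safety changes are part of the phase 1b primary endpoint, and the AMG 592 groups are small: 6 in cohorts 1 and 4, and 12 in cohorts 2 and 3 if expanded. One wrongly graded subject is visible in a cohort table.

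**Working it through.** The documents give no figure for the effect of this rule, so there is none to reproduce. The check has three parts.

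**1. Width of the windows.** From the chemistry and haematology table in SAP Appendix E, with the week 12 dose on day 85. For weeks 4, 6 and 8 the target day is 7n + 1 and the window runs from target − 6 to target + 7.

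| Target day | Window (days) | Width |
|---|---|---|
| 2 | 2–3 | 2 |
| 8 | 4–12 | 9 |
| 15 | 13–22 | 10 |
| 29 | 23–36 | 14 |
| 43 | 37–50 | 14 |
| 57 | 51–64 | 14 |
| 71 | 65–78 | 14 |
| 85 | 79–92 | 14 |
| 99 | 93–106 | 14 |
| 113 | after 106 | open-ended |

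With the week 12 dose on day 84, 85 or 86, each day from 2 to 127 falls in exactly one window. The windows from day 23 to day 106 are then 13 to 15 days wide. A central sample on its target day can therefore displace local results from 6 days before it to 7 days after it.

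**2. Direction of any error.** Let A be all post-dose results for a subject and parameter, and B the results left after the rule. B is a subset of A, so max(B) ≤ max(A). The rule can lower the worst grade but cannot raise it.

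**3. Illustration, all values assumed.**

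- Central ALT: 1.5 × ULN on day 29 and 1.2 × ULN on day 43.
- Local ALT: 8.5 × ULN on day 31, 6.0 on day 33 and 3.5 on day 36.
- All three local results fall in days 23–36, which hold the day 29 central result, so the literal rule excludes them.
- Maximum under the literal rule: max(1.5, 1.2) = 1.5 × ULN.
- Maximum over all post-dose results: 8.5 × ULN.

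If the grade 3 or higher listing is triggered from the same filtered data, the local peak does not trigger it either.

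**Scale per subject.** One wrongly graded subject on AMG 592 is 1/6 = 16.7 percentage points in cohort 1 or 4, and 1/12 = 8.3 points in cohort 2 or 3. These figures do not estimate how often it would happen.

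**Limits.** Protocol Table 2-2 schedules no chemistry at weeks 14 and 16, so no scheduled central chemistry displaces a local value there. INR is not in the analyte list in Protocol Appendix 2, so no central INR is planned.

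**The case against.** The strongest reply is that the sentence sits in an appendix on visit windows. SAP 5.2.1 gives the purpose of that mapping: actual visits may miss their scheduled dates. On that view, both the source rule and the closest-to-target rule choose a value for each visit and do not touch a maximum. SAP 9.1 and 9.6.3 also lean towards including unscheduled data. This is a fair reading and may be what was intended, but the text does not say so. The source rule speaks of analysis without qualification, and 9.6.3 does not say whether the maximum is taken over all records or over the one kept in each window.

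A reader might infer that Appendix E is the exception that SAP 9.1 allows for. That goes too far: 9.1 concerns unscheduled data, while the source rule concerns laboratory. An unscheduled central result is untouched by the source rule, though the closest-to-target rule could drop it.

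A reader might also infer that emergency and liver-retest samples are local and so drop out. No section says this. Protocol 9.2.4 makes central testing the default, Appendix 7 names no laboratory, and the requirement to record results in CRFs does not show where they were measured. Local testing is possible, but its frequency is unknown.

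There are also backstops:

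- Under Protocol 9.2.4, investigators record clinically relevant laboratory changes, and changes needing treatment are adverse events. This depends on judgment, and where applicable the clinical sequelae are recorded in place of the laboratory finding.
- Appendix 7 requires serious adverse event reports for concurrent AST or ALT and bilirubin and/or INR elevation, but not automatically for an isolated enzyme peak.
- Dose decisions rest on the dose level review, which has its own analysis plan and sees all available data, not on these end-of-study tables.

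These limit the consequence but do not correct the shift tables.

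**Conclusion.** The point holds in conditional form. As written, Appendix E can exclude a local result from the maximum post-dose grade, the shift tables and the listing trigger whenever a central result lies in the same window. If applied that way, it conflicts with Protocol 10.3.2.3.3 and is an undeclared change from the protocol.

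Any error understates the worst grade. Its size ranges from zero, if no displaced local result exceeds the subject's central maximum, to a lower worst grade for each subject whose peak is a displaced local result. The documents do not allow anything narrower. Inferring the share of local results lost from visit attendance would only restate an assumed attendance rate.

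A reader might conclude that toxicity will be understated. The documents support only that it may be, in one type of table and its linked listing. The conclusion assumes that some chemistry or haematology is measured locally after dosing and that the rule is programmed as worded.

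**What to change.** Amend SAP Appendix E to state that:

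- the central-over-local rule and the closest-to-target rule apply to by-visit summaries only;
- the maximum post-dose grade, the shift tables and the trigger for the grade 3 or higher listing use every post-dose result, central or local, scheduled or unscheduled;
- local results are graded against the reference range of the laboratory that reported them.

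Include the closest-to-target rule in the same change. Otherwise a central retest taken away from the target day could be lost in the same way.

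The cost is a sentence or two in the SAP and a small programming change. Local reference ranges must be captured with the results, and worst values will carry slightly more between-laboratory variability. If the sponsor does intend to exclude local results from the worst grade, SAP Section 10 should declare and justify that as a change from the protocol.

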1. INTRODUCTION

- **Replaced:** protocol date of 26 June 2017 **with** date 06 June 2019.

3. Study Overview

Updates to sections below reflect changes in the protocol

- **3.1 Study Design**

Phase 1b:

Added:

Cohort 3 dose changed to [REDACTED]

Approximately 8 additional subjects (6 AMG 592; 2 placebo) may be enrolled into each of cohorts 2 and 3.

For cohorts 2 and 3 an additional DLRM will convene after the first 16 enrolled subjects (8 in each cohort) complete the week 4 visit.

- **3.2 Sample Size**

Phase 1b

Sample size was increased from 32 to 48 subjects. 16 subjects were added to Cohorts 2 and 3.

Added:

Approximately 48 subjects will be randomized. 8 subjects randomized to each of cohorts 1 and 4 and approximately 16 subjects randomized to each of cohorts 2 and 3. The total sample size may be higher than 48 subjects if, DLRM recommended additional dosing cohorts and/or expansion of existing cohorts or replacement of subject. Additional subjects may be enrolled in each cohort to enable all screened eligible subjects to

participate in the study. Within each cohort subjects will be randomized to AMG 592 or placebo in a 3:1 ratio.

In case of expansion of cohorts 2 and 3, with 12 subjects receiving AMG 592 in cohort 2 and 3, the chance of at least 1 subject experiencing an adverse event within that cohort increases to 97% and 93% for true event rates of 25% and 20%, respectively. In addition, with a total of 36 subjects planned to receive AMG 592 in the phase 1b part of the study in case of expansion of cohorts 2 and 3, the chance of at least 1 subject experiencing an adverse event across the cohorts increases to 30% and 84% if the true event rates are 1% and 5%, respectively.

5. Definitions

Updates to sections below include additions of new definitions or updates to existing definitions to bring more clarity to the analysis.

- **5.1 Basic Definitions**

[REDACTED]

[REDACTED]

[REDACTED]

5.2 Study Points of Reference

5.2.1 Phase 1b

Replaced:

Baseline

The last measurement for the endpoint of interest taken before the first dose of investigational product in phase 1b of this study.

With:

Baseline

The last measurement for the endpoint of interest taken prior to or on the first dose of investigational product in phase 1b of this study, unless stated otherwise.

Deleted: Study Visit Table corresponding to analysis visit windows. Instead added revised tables for analytical windows in Appendix E.

[REDACTED]

[REDACTED]

[5.3 Definitions of Study Endpoints](#)

Added: Definitions for ECG Analysis Value, Baseline ECG, Changes from Baseline, Percent Change from Baseline, Fold Change from Baseline, Improvements from Baseline, Percent Improvement from Baseline, [REDACTED]

[REDACTED] Adverse Events, Treatment Emergent Adverse Event, Disease Related Adverse Events, Prior and Concomitant medications were added.

ECG analysis value

ECGs will be performed in triplicate, approximately 30 seconds apart, at time points specified in the Schedule of Assessments in the protocol. On day -1 baseline, three sets of triplicate ECGs will be collected, with each set being \geq 30 minutes apart (i.e. total of 9 ECGs). At other time points single triplicate ECGs will be collected. The mean value of each triplicate will be calculated and used in the analysis. If an ECG is missing within a

triplicate, all available data will be averaged for that time point. Further, unscheduled ECG measurements taken up to 5 minutes after the last assessment of a triplicate at a time point will be included in the mean for that time point

Baseline ECG

The baseline ECG is defined as the average of the mean of the triplicates at Day -1; the mean of values in a triplicate should be calculated before taking the mean of the triplicate averages.

Changes from Baseline

Change from Baseline is the arithmetic difference between post-Baseline and Baseline.

Percent Change from Baseline

[figure not shown]
Percent change from Baseline is the arithmetic difference between post-Baseline and Baseline and Baseline divided by Baseline values times 100. If the change from baseline is not equal to 0 and the baseline value is 0 then percent change is not defined. If the change from baseline is equal to 0 and the baseline value is also 0 then percent change is 0.

[figure not shown]
Fold change from Baseline

Fold change from Baseline equals the post- Baseline value divided by the Baseline value. If the change from Baseline is not equal to 0- and the baseline value is 0 then fold change is not defined. If the change from baseline is equal to 0 and the baseline value is also 0 then fold change is 1.

Improvement from Baseline

For endpoints where, higher score indicates better clinical outcome, improvement is defined as post-baseline value-baseline. For endpoints where, lower score indicates better clinical outcome, improvement is defined as baseline value post-baseline value.

Adverse Event

This includes all adverse events/serious adverse events and disease-related events as identified on the Adverse Events eCRF.

Treatment Emergent Adverse Events (TEAE)

Revised the definition to match with Amgen standard definition of TEAE

Replaced:

Adverse events that occurred after first dose of investigational product in the current study period

With:

A treatment emergent adverse event is any adverse event (including disease-related events) starting on or after the first dose of investigational product (as determined by the flag indicating if the adverse event started prior to the first dose or not on the Adverse Events eCRF) and up to and including 42 days after the end of investigational product or the End of study date, whichever is earlier.

Disease Related Event

Events anticipated to occur in the study population due to the underlying disease. Protocol lists joint pain, joint stiffness, joint swelling, and worsening of rheumatoid arthritis as disease related events. These will be identified on the Adverse Event eCRF.

Prior and Concomitant medications

Prior medication is defined as any medication that with start date prior to the first dose date of study drug. Concomitant medication is defined as any medication with start date prior to the first dose date of study drug but which continued to be taken after the first

dose of study drug or any medication that with start date on or after the first dose date and up to and including 42 days after the last dose date.

6. Analysis Sets

